7.0 Evaluation during Study

Clinic visits (this will include vital signs and physical exam) at The University of Texas, M.D. Anderson Cancer Center are required at the end of cycles 3, 7, 13, 19, 23, and every 6 cycles (\pm 14 days) after that. Hematology complete blood counts (white blood cell, hemoglobin, platelets and differential) will be monitored once weekly (\pm 3 days) for the first five weeks and once every two weeks (\pm 5 days) in case of dose increase until a stable dose of lenalidomide has been established for the specific patient (the once every two weeks laboratory monitoring will not apply if the dose is decreased for non-hematological or laboratory measurable toxicity), and then every four weeks (once per cycle) thereafter. Pregnancy testing and counseling per the RevAssist® program. Serum chemistry basic metabolic profile, (sodium, potassium, chloride, CO₂, BUN, creatinine, uric acid, calcium and phosphorus, ALT, AST, alkaline phosphatase, (bilirubin and glucose) will be monitored once weekly (\pm 3 days) for the first five weeks and then once every two weeks (\pm 5 days) until a stable dose of lenalidomide has been established for the specific patient and then every four weeks (once per cycle) thereafter. Additional laboratory evaluations may be obtained after the first dose of lenalidomide, in week 2 of cycle 1 and at any time during the study if clinically indicated. TSH, beta-2-microglobulin, lymphocyte subset, immunoglobulin levels, bone marrow biopsy and aspiration will be performed at the end of cycles 3, 7, 13, 19, 23, and every 6 cycles after that (\pm 14 days). If patients continue on the study past 24 cycles a bone marrow biopsy and aspirate (with flow cytometry and molecular studies if indicated) to check the status of the disease will be obtained once every 6-12 cycles (\pm 28 days) as clinically indicated and blood will also be drawn for routine tests. Electrocardiogram will be conducted as clinically indicated during and after treatment.

In subjects that are HBsAg negative, HBcAb positive and have a negative HBV DNA testing at study entry monitoring for hepatitis B reactivation by HBV DNA PCR testing is required during the on treatment periods at least every 2 months and during follow up at a minimum of every 2-3 months up to 6 months after the last dose of ofatumumab.

Once treatment has been completed or discontinued, liver function test (ALT, AST, alkaline phosphatase and bilirubin) will be performed 6 months (\pm 28 days) after the last dose of ofatumumab has been administered unless patients have received subsequent treatment for their CLL. Correlative laboratory studies and Quality of Life questionnaire (Appendix E) are optional and if the patient agrees they will be collected at baseline, at the end of cycles 3, 7, 13, 19, 23 and every 6 cycles after that (\pm 14 days).

You will be required to use TWO reliable forms of birth control, one highly effective method and one additional effective method at the same time or

practice complete abstinence from heterosexual intercourse during the following time periods related to this study: 1) for at least 28 days before starting lenalidomide; 2) while participating in this study; and 3) for at least 28 days after discontinuation from the study. The following are the acceptable birth control methods:

Highly Effective Methods	Additional Effective Methods
Intrauterine device (IUD)	Latex condom
Hormonal (birth control pills, injections, implants)	Diaphragm
Tubal ligation	Cervical Cap
Partner's vasectomy	

Females must not breastfeed a baby while participating in this study and for at least 28 days after you have been discontinued from the study.

Females of childbearing potential with regular or no menstrual cycles must agree to have pregnancy tests weekly for the first 28 days of study participation and then every 28 days while on study, at study discontinuation, and at day 28 following discontinuation from the study. If menstrual cycles are irregular, the pregnancy testing must occur weekly for the first 28 days and then every 14 days while on study, at study discontinuation, and at days 14 and 28 following discontinuation from the study.

8.0 Criteria for Response

The 1996 NCI Working Group criteria will be used. (See Appendix F). Responses will be assessed after 3, 7, 13, 19 and 23 cycles and every 6-12 months as clinically indicated.

9.0 Evaluation of Toxicity

Adverse events are reported as per UTMDACC and Leukemia Phase 2-3 studies (Appendix H and Appendix I).

Adverse Events with Lenalidomide

Most frequently reported adverse events reported during clinical studies with lenalidomide in oncologic and non-oncologic indications, regardless of presumed relationship to study medication include: anemia, neutropenia, thrombocytopenia and pancytopenia, abdominal pain, nausea, vomiting and diarrhea, dehydration, rash, itching, infections, sepsis, pneumonia, UTI, upper respiratory infection, cellulitis, atrial fibrillation, congestive heart failure, myocardial infarction, chest pain, weakness, hypotension, hypercalcemia, hyperglycemia, back pain, bone pain, generalized pain, dizziness, mental status changes, syncope, renal failure, dyspnea, pleural effusion, pulmonary embolism, deep vein thrombosis, CVA,

convulsions, dizziness, spinal cord compression, syncope, disease progression, death not specified and fractures.

Please refer to lenalidomide package insert or Investigator Brochure for a complete list.

Adverse Events with Ofatumumab

The following reactions should be regarded as expected infusion-related adverse reactions in connection with the use of ofatumumab as a consequence of B-lymphocyte depletion: pruritus, dyspnea, bronchospasm, throat irritation, cough, pharyngolaryngeal pain, flushing, hyperhidrosis, nausea and vomiting, abdominal pain, hypotension, rash/urticaria, influenza-like-illness, fatigue, fever, chills, headache, dizziness, myalgia and arthralgia. Profound and long-lasting depletion of CD20+ B lymphocytes has been seen during treatment with ofatumumab as expected with an anti-CD20 antibody, but so far without any signs of an increased risk of infectious complications. In all clinical studies adverse events were reported with substantially higher frequency on the first infusion day, compared to the subsequent infusions.

Further information can be found in the Ofatumumab Investigator's Brochure.

Myelosuppression and associated complications are expected events during leukemia therapy and are part of the treatment success (marrow emptying of leukemic cells). Therefore, myelosuppression and associated complications such as fever, infections, bleeding and related hospitalizations will not be reported as individual adverse drug reactions (ADRs), but will be summarized in the updated and final reports. Only prolonged myelosuppression, as defined by the new NCI criteria specific for leukemia, i.e., marrow cellularity < 5% on day 42 or later (6 weeks) from start of therapy without evidence of leukemia, will be reported.

MD Anderson (Sponsor) Reporting Requirements for Serious Adverse Events and Dose Limiting Toxicities:

Serious Adverse Event (SAE) Definition

A serious adverse event is one that at any dose (including overdose):

- Results in death
- Is life-threatening¹
- Requires inpatient hospitalization or prolongation of existing hospitalization
- Results in persistent or significant disability or incapacity²
- Is a congenital anomaly or birth defect
- Is an important medical event³

¹“Life-threatening” means that the subject was at immediate risk of death at the time of the serious adverse event; it does not refer to a serious adverse event that hypothetically might have caused death if it were more severe.

²“Persistent or significant disability or incapacity” means that there is a substantial disruption of a person’s ability to carry out normal life functions.

³Medical and scientific judgment should be exercised in deciding whether expedited reporting is appropriate in situations where none of the outcomes listed above occurred. Important medical events that may not be immediately life-threatening or result in death or hospitalization but may jeopardize the patient or may require intervention to prevent one of the other outcomes listed in the definition above should also usually be considered serious. Examples of such events include allergic bronchospasm requiring intensive treatment in an emergency room or at home, blood dyscrasias or convulsions that do not result in inpatient hospitalization, or the development of drug dependency or drug abuse. A new diagnosis of cancer during the course of a treatment should be considered as medically important.

Adverse Drug Reaction Reporting

AS PER UTMDACC AND LEUKEMIA PHASE II-III STUDIES (APPENDIX H AND APPENDIX I), Toxicity will be scored using CTCAE Version 3.0 for toxicity and adverse event reporting and myelosuppression will be reported according to the recommended guidelines for CLL (Appendix J). A copy of the CTCAE Version 3.0 can be downloaded from the CTEP homepage (<http://ctep.info.nih.gov>). All appropriate treatment areas should have access to a copy of the CTCAE Version 3.0. All adverse clinical experiences (according to Appendix H), whether observed by the investigator or reported by the patient, must be recorded, with details about the duration and intensity of each episode, the action taken with respect to the test drug, and the patient’s outcome. The investigator must evaluate each adverse experience for its relationship to the test drug and for its seriousness.

The investigator must appraise all abnormal laboratory results for their clinical significance. If any abnormal laboratory result is considered clinically significant, the investigator must provide details about the action taken with respect to the test drug and about the patient’s outcome. Abnormal lab values are only significant if they require intervention or treatment.

Serious Adverse Events Reporting: The principal investigator has the obligation to report all serious adverse events to The University of Texas M. D. Anderson Cancer Center (MDACC) IRB via the Office of Protocol Research in accordance with the timeframes and procedures outlined in “The University of Texas M. D. Anderson Cancer Center Institutional Review Board Policy on Reporting Serious Adverse Events and to Celgene and GSK within 24 hours.

All events occurring during the conduct of a protocol and meeting the definition of a SAE must be reported to the IRB in accordance with the timeframes and procedures outlined in "The University of Texas M. D. Anderson Cancer Center Institutional Review Board Policy on Reporting Serious Adverse Events". Unless stated otherwise in the protocol, all SAEs, expected or unexpected, must be reported to ORERM, regardless of attribution (within 5 working days of knowledge of the event).

All life-threatening or fatal events, expected or unexpected, and regardless of attribution to the study drug, must have a written report submitted within **24 hours** (next working day) of knowledge of the event to the Safety Project Manager in ORERM.

The MDACC "Internal SAE Report Form for Prompt Reporting" will be used for reporting to ORERM.

Serious adverse events will be captured from the time the patient signs consent until 30 days after the last dose of lenalidomide and for a minimum of 5 half lives (6 months) after the last dose of ofatumumab. If a subject does start other therapy, then SAEs will no longer be required to be reported.

Serious adverse events must be followed until clinical recovery is complete and laboratory tests have returned to baseline, progression of the event has stabilized, or there has been acceptable resolution of the event.

Additionally, any serious adverse events that occur after the 30 day time period that are related to the study treatment must be reported to ORERM. This may include the development of a secondary malignancy.

Reporting to FDA:

Serious adverse events will be forwarded to FDA by the IND Sponsor (Safety Project Manager ORERM) according to 21 CFR 312.32.

It is the responsibility of the PI and the research team to ensure serious adverse events are reported according to the Code of Federal Regulations, Good Clinical Practices, the protocol guidelines, the sponsor's guidelines, and Institutional Review Board policy.

NOTE: Instructions concerning procedures and reporting for pregnancies below.

Pregnancies

Pregnancy of a female subject or the female partner of a male subject occurring while the subject is on lenalidomide and ofatumumab or within 4 weeks after the

subject's last dose of lenalidomide or ofatumumab are considered expedited reportable events. If the subject is on lenalidomide, it is to be discontinued immediately and the subject is to be instructed to return any unused portion of lenalidomide to the Investigator. The pregnancy must be reported by the investigator to MDACC IRB and ORERM AND to Celgene Corporation Worldwide Drug Safety Surveillance (WWDSS) and to GSK within 24 hours of the Investigator's knowledge of the pregnancy by phone and facsimile using the SAE Form.

The Investigator will follow the subject until completion of the pregnancy, and must notify Celgene Corporation Worldwide Drug Safety Surveillance (WWDSS) of the outcome as specified below. The Investigator will provide this information as a follow-up to the initial SAE.

If the outcome of the pregnancy meets the criteria for immediate classification as a SAE (i.e., spontaneous abortion [any congenital anomaly detected in an aborted fetus is to be documented], stillbirth, neonatal death, or congenital anomaly), the Investigator should follow the procedures for reporting SAEs (i.e., report the event to Celgene Corporation Worldwide Drug Safety Surveillance (WWDSS) by facsimile within 24 hours of the Investigator's knowledge of the event) and report the event to MDACC IRB and ORERM.

Any suspected fetal exposure to lenalidomide must be reported to Celgene, GSK, MDACC IRB AND ORERM within 24 hours of being made aware of the event. The patient should be referred to an obstetrician/gynecologist experienced in reproductive toxicity for further evaluation and counseling.

All neonatal deaths that occur within 30 days of birth should be reported, without regard to causality, as SAEs. In addition, any infant death after 30 days that the Investigator suspects is related to the in utero exposure to lenalidomide should also be reported.

In the case of a live "normal" birth, Celgene Corporation Worldwide Drug Safety Surveillance (WWDSS), GSK, MDACC IRB AND ORERM should be advised as soon as the information is available.

Drug Safety Contact Information:

Celgene Corporation
Worldwide Drug Safety Surveillance (WWDSS)
[name]
[name]

Toll Free: [contact]

[contact]
[contact]
e-mail: [contact]

GlaxoSmithKline
[name]
[name]
[contact]
E-mail: [contact]

Investigator Reporting Responsibilities

The conduct of the study will comply with all FDA safety reporting requirements. Serious Adverse Events Reporting: The principle investigator has the obligation to report all serious adverse events to the University of Texas M. D. Anderson Cancer Center (MDACC) IRB via the Office of Protocol Research in accordance with the timeframes and procedures outlined in "The University of Texas M. D. Anderson Cancer Center Institutional Review Board Policy and also to Celgene and GSK within 24 hours.

IND Annual Reports

If the FDA has granted an IND number, it is a requirement of 21 CFR 312.33, that an annual report is provided to the FDA within 60-days of the IND anniversary date. 21 CFR 312.33 provides the data elements that are to be submitted in the report. The Annual Report should be filed with MD Anderson's ORERM, who will then forward to FDA. An additional copy should be placed in the study's Regulatory Binder and a copy must be sent by the PI/research team to Celgene and GSK as supporters of this study as follows.

Celgene Corporation
Attn: Medical Development
[name]
[name]
[contact]

GlaxoSmithKline
[name]
[name]
[contact]

All adverse experience reports must include the patient number, age, sex, severity of reaction (mild, moderate, severe), relationship to study drug (probably related, unknown relationship, definitely not related), date and time of administration of test medications and all concomitant medications, and medical

treatment provided. The investigator is responsible for evaluating all adverse events to determine whether criteria for “serious” and as defined above are present. The investigator is responsible for reporting adverse events to Celgene and GSK as described below.

Expedited reporting by Principal Investigator to Celgene and GSK

Serious adverse events (SAE) are defined above. The investigator should inform Celgene and GSK of any SAE within 24 hours of being aware of the event. The date of awareness should be noted on the report. This must be documented on an MD Anderson SAE form. This form must be completed and supplied to Celgene and GSK within 24 hours/1 business day at the latest on the following working day. The initial report must be as complete as possible, including details of the current illness and (serious) adverse event, and an assessment of the causal relationship between the event and the investigational product(s). Information not available at the time of the initial report (e.g., an end date for the adverse event or laboratory values received after the report) must be documented on a follow-up MD Anderson SAE form. A final report to document resolution of the SAE is required. The Celgene protocol number (RV-CLL-PI-0468) should be included on SAE reports to Celgene. A copy of the fax transmission confirmation of the SAE report to Celgene and GSK should be attached to the SAE and retained with the patient records.

Report of Adverse Events to the Institutional Review Board

The principal Investigator is required to notify his/her Institutional Review Board (IRB) of a serious adverse event according to institutional policy.

Sponsor Reporting to the FDA

Adverse drug reactions that are Serious, Unlisted/unexpected, and at least possibly associated to the drug, and that have not previously been reported in the Investigators brochure, or reference safety information document should be reported promptly to the Food and Drug Administration (FDA) in writing by each investigator/physician engaged in clinical research. A clear description of the suspected reaction should be provided along with an assessment as to whether the event is drug or disease related.

The sponsor shall notify the FDA by telephone or by fax of any unexpected fatal or life threatening experience associated with the use of the drug. As soon as possible, but no later than 7 calendar days after the sponsors initial receipt of the information. Each phone call or fax shall be transmitted to the FDA new drug review division in the Center for Drug Evaluation and Research or the product review division in the Center for Biologics Evaluation and Research that has responsibility for review of the IND if applicable.

Adverse event updates/IND safety reports

Celgene and GSK shall notify the Investigator via an IND Safety Report of the following information:

1. Any AE associated with the use of study drug in this study or in other studies that is both serious and unexpected.
2. Any finding from tests in laboratory animals that suggests a significant risk for human subjects including reports of mutagenicity, teratogenicity, or carcinogenicity.

The Investigator shall notify his/her IRB/EC promptly of these new serious and unexpected AE(s) or significant risks to subjects.

The Investigator must keep copies of all AE information, including correspondence with Celgene and the IRB/EC, on file.

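### The end of SAE reporting at the start of other therapy has no exception for treatment-related events, so it conflicts with the late related-event rule and leaves a gap in the first 30 days

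*Combined protocol and SAP*

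**What the plan says.** Section 9.0 (Evaluation of Toxicity) opens SAE collection at consent. With respect to lenalidomide it runs "until 30 days after the last dose of lenalidomide". With respect to ofatumumab the period is longer: "for a minimum of 5 half lives (6 months) after the last dose of ofatumumab". The next sentence is the cut-off: "If a subject does start other therapy, then SAEs will no longer be required to be reported". It does not mention attribution, and other therapy is not defined.

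A little further on, the same section adds that "any serious adverse events that occur after the 30 day time period that are related to the study treatment must be reported to ORERM", and continues: "This may include the development of a secondary malignancy". This rule has no end date and does not mention other therapy.

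Four other provisions bear on the point:

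- Section 9.0, Adverse Drug Reaction Reporting, gives the general duty: "Unless stated otherwise in the protocol, all SAEs, expected or unexpected, must be reported to ORERM, regardless of attribution". It then requires a written report of every life-threatening or fatal event within 24 hours, whatever the attribution, and states no cut-off there.
- Section 9.0, on expedited reporting to Celgene and GSK, asks for any SAE within 24 hours of awareness and does not repeat the cut-off.
- Section 9.0, Sponsor Reporting to the FDA, covers reactions that are serious, unexpected and at least possibly drug-associated, again without a cut-off.
- Section 7.0 waives the 6-month liver function test "unless patients have received subsequent treatment for their CLL". It continues hepatitis B DNA testing in at-risk patients to 6 months after ofatumumab without that exception.

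**The concern.** The cut-off and the late related-event rule give opposite instructions for the same event. If a patient starts new therapy and later has a related SAE or a second cancer, one sentence removes the duty to report and the other imposes it. An investigator can comply with the first and breach the second.

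The patients affected are not a random subset. Those who stop for progression or intolerance are the likely ones to start another treatment, so whether safety data are collected would depend on outcome. Tolerance is the secondary endpoint (Section 1.0) and the trial plans only 36 patients (Section 10.0), so a few missing related events could change the late safety picture. Section 9.0 also makes ORERM the route by which SAEs are forwarded to FDA, so an event that never reaches ORERM is not forwarded by that route.

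**Working it through.** The plan states no figure to reproduce. The check is a side-by-side reading of the rules, followed by one illustration of size.

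**Step 1. Apply the two Section 9.0 rules to a patient who has already started other therapy.** The only 30-day period that the section defines is the one after the last lenalidomide dose.

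| Event | Cut-off sentence | Late related-event rule | Result |
|---|---|---|---|
| Unrelated SAE inside the 6-month ofatumumab window | Not required | Does not apply | Not required; consistent |
| Related SAE within 30 days | Not required | Not yet in force | Covered by neither: a gap |
| Related SAE or second cancer after 30 days | Not required | Must be reported | Direct conflict |

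The gap has an odd consequence. If the late rule is taken to prevail over the cut-off, a related hospitalization on day 40 is reportable, but the same event on day 20 is not.

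**Step 2. Compare with the other reporting rules.**

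- The general duty to report to ORERM yields to anything stated otherwise in the protocol. The cut-off is such a statement, so it can switch that duty off.
- The rule on life-threatening and fatal events carries no such proviso where it stands, and the rule on reports to the suppliers covers any SAE. Both disagree with the cut-off for a patient on new therapy.
- The FDA rule still reaches serious, unexpected, possibly associated reactions. It does not reach related events that are already expected.
- Hepatitis B DNA testing continues to 6 months whether or not new therapy has started. The plan thus looks for reactivation in patients whose serious reactivation the cut-off, read literally, need not be reported.

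**Step 3. Illustrate how much of the ofatumumab window the cut-off can remove.** Inputs: the 6-month window from Section 9.0, taken as 183 days (assumption), and the day *d* after the last ofatumumab dose on which other therapy starts (assumption; the documents give no distribution).

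Share of window removed = (183 − *d*) / 183

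- *d* = 30: 153 / 183 = 84%
- *d* = 90: 93 / 183 = 51%
- *d* = 150: 33 / 183 = 18%

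These are shares of calendar time, not of events. For related events they describe a loss only if the cut-off is read as prevailing.

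**Step 4. Check what the analysis plan uses.** The primary outcome is overall response, so the Simon two-stage design does not draw on SAE reports. The Bayesian toxicity boundary counts grade 3–4 non-hematological toxicity, and Section 10.0 excludes events after cycle 6. Any effect there would be limited to patients who leave treatment before that point.

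**The case against.** The best defence is that the rules can be read together. The cut-off directly follows the collection window and reads as an exception to it. The parallel waiver in Section 7.0 suggests that this was intended, and ending all-cause collection once a new drug confounds attribution is a defensible choice. The late rule comes afterwards, is introduced as an addition, has no end date and names second cancers. On that reading, all-cause collection stops at new therapy while late related events stay reportable.

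Much of this stands, and it rules out several stronger readings:

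- A reader might infer that the cut-off flatly contradicts the 6-month window. It sits awkwardly with a period described as a minimum, but an exception that shortens the window is the more natural reading.
- A reader might infer that all late related events and second cancers are lost. The text does not clearly direct that, because the late rule can be read as preserving them and the fatal-event, supplier and FDA rules are partial backstops. A fatal infection in particular remains within the rule on life-threatening and fatal events.
- A reader might infer that starting the late rule at 30 days, rather than at 6 months, loses events. It does not: the earlier start overlaps the ofatumumab window.
- A reader might infer that every patient who changes therapy is affected. Section 4.0 allows lenalidomide beyond 24 cycles, after ofatumumab has ended. A patient who starts new therapy once both windows have closed loses nothing from them.

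The defence does not close the gap for related SAEs inside 30 days. It also relies on a priority between two unqualified sentences that the protocol never states. The appendices and institutional policy to which reporting is referred are not in the material available and might clarify the point; the protocol text itself does not.

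**Conclusion.** The point holds as a drafting conflict with a real but limited consequence. Section 9.0 gives incompatible instructions for related SAEs and second cancers more than 30 days out once other therapy has begun, and its two timing rules leave related SAEs within 30 days uncovered. Under-reporting is possible, not certain.

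The window removed ranges from 84% to 18% for new therapy starting between day 30 and day 150. This rests on a 183-day window and on assumed start dates, and it cannot be turned into a number of missed events from the documents. The primary endpoint and the Simon design are untouched, and the toxicity boundary could be affected only through patients who leave before the end of cycle 6. What is exposed is the completeness of the safety description. Severity is moderate to low.

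**What to change.** Reword the cut-off in Section 9.0, for example: *Once a subject starts other treatment for CLL, SAEs assessed as unrelated to both lenalidomide and ofatumumab are no longer reportable. SAEs assessed as related to either drug, at any time after the last dose, and any secondary malignancy remain reportable.*

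In addition:

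- Define other therapy in the same terms as the Section 7.0 liver-test waiver, that is, subsequent treatment for CLL.
- Reconcile the Section 9.0 rules on the general reporting duty, life-threatening and fatal events, supplier reports and FDA reports with the reworded sentence, so that each states whether the cut-off applies.

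The start date of the late rule need not move to recover events. All-cause death reporting after new therapy is not needed to resolve the conflict. It would add follow-up that the documents do not describe for these patients.

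The cost is a wording amendment and a few more related-event reports. No visits or procedures are added.
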